## 11.0 Setting

Participants will be screened for eligibility via phone and data will be entered into REDCap. All screening data will be collected online via REDCap. The study investigators will be the only ones who have access to the data collection portal. Qualitative interviews will be recorded and transcribed for analysis.

## 12.0 Risks to Subjects

**FULL PROTOCOL TITLE:** Mobile Health to Monitor Risk for COVID-19 and Improve Mental Health during the Pandemic

Participation in this study poses minimal risk to participants. However, one potential, although unlikely, risk to participants is loss of confidentiality. The severity of harm in the case of loss of confidentiality may range from mild to severe depending upon the individual and the specific circumstances. However, the risks of participation in the study are similar to participation in usual in person mental health clinic care, as loss of confidentiality may be experienced in either case. Other possible adverse events might include compromised data security and discomfort related to being asked study questions. The research team will monitor this risk and the others listed below and report adverse events immediately to the IRB.

Each participant will be assigned an identification number that will be utilized in place of names in all electronic data files. The sheet or datafile containing the links between participant names and identifiers will be kept in locked filing cabinet and/or password protected digital files on encrypted university computers and will be destroyed 12 months after data collection has been completed. All electronic data (with names omitted) will be maintained on the investigator's computers, and all computers and electronic files will be encrypted and password protected. Identifiable participant information will not be released to any party outside the research team at any time.

In the unlikely event that a participant experiences severe symptoms while participating in the study, a protocol has been developed to address this concern. If a participant experiences severe symptoms, mental health referral information for providers within a 50-mile radius of their home location will be provided to participants. The potential for discomfort associated with being asked personal questions regarding thoughts and behaviors will be minimized in the following ways:

- i. By informing participants of the nature of questions to be asked, participants will not be caught unaware by the topics covered and can decline participation if such topic areas are known to be personally uncomfortable.
- ii. Only measures that have been validated or used in prior studies will be used. None of the proposed instruments have been known to evoke serious emotional reactivity.
- iii. Participants will be consistently reminded that they are free to skip any baseline/follow-up questions they do not wish to answer, without penalty.
- iv. All participants will be reminded during consent they may contact study staff with any questions or concerns that arise during the survey.

Lastly, the time commitment to participate in the study may be burdensome to participants. However, participants will be informed that they can leave the research at any time it will not be held against them.

### **13.0 Potential Benefits to Subjects**

First, the overall cost/benefit ratio is highly favorable for participants. All participants will have the opportunity to examine and improve their ability to effectively manage their mood and stress through the intervention program. Second, the costs of completing the study have been minimized through our use of procedures for maintaining confidentiality, and minimizing the risk of adverse study reactions. Third, the societal benefits of the proposed research are better

**FULL PROTOCOL TITLE:** Mobile Health to Monitor Risk for COVID-19 and Improve Mental Health during the Pandemic

understanding how to develop a mobile mental health intervention that is personalized and focused on improving anxiety and depression. Fourth, the implementation of smartphone-based interventions to address anxiety and depression could have a positive impact on public health policy for minorities (e.g., American Indians, Hispanic, African Americans). Further, it is possible that EMAs will identify key factors that predict mental health symptom exacerbation, and this information may be used to improve future COVID-19-specific mental health interventions for White, African Americans, Hispanic, and American Indians. Finally, all participants, regardless of group assignment, will complete a daily COVID-19 screener. This information will have access to a COVID-19 symptom screener and when our previously developed algorithm indicates heightened risk, participants will be notified and assisted (if desired) with scheduling a COVID-19 test.

## **14.0 Withdrawal of Subjects**

There are no anticipated circumstances under which subjects will be withdrawn from the research without their consent.

## **15.0 Costs/Payments to Subjects**

In addition to compensating participants for completing the Baseline (i.e., \$20), and 3- and 6-month post-baseline assessments, which will include a qualitative interview over the phone for selected participants (i.e., \$50 each), participants will be compensated for completing daily EMAs for 6-months. Specifically, those who complete 50%-74% of prompted EMAs each month (2 per day x 30 days = 60 monthly EMAs) will receive \$20, those who complete 75%-89% of assessments will receive \$30, and those who complete 90% or more of their EMAs will receive a total of \$40 for that month. Additionally, participants will have the ability to earn up to \$50 for referring people to our study. Participants will have the ability to earn \$10 for each person they refer who is deemed eligible and randomized into the study, up to \$50. Participants will be compensated through a reloadable Greenphire MasterCard. These cards can be used anywhere MasterCard is accepted and participants may use these cards to withdraw their compensation from a bank. This convenient and auditable method of payment is preferred by participants and study staff. Cards will be purchased by the study team and mailed to participants following their baseline assessment and reloaded monthly based upon compensation earned.

## **16.0 Confidentiality**

Consent forms with identifying information will be completed via RedCap, encrypted, and stored on university computers. A password protected computer file will contain information linking participant names to their assigned numbers. Only the researchers will have access to this information.

## **17.0 Provisions to Protect the Privacy Interests of Subjects**

Participants will be consistently reminded that they are free to skip any baseline/follow-up questions they do not wish to answer, without penalty. Participants will not need to answer any questions that they find intrusive to their privacy.

## **FULL PROTOCOL TITLE: Mobile Health to Monitor Risk for COVID-19 and Improve Mental Health during the Pandemic**

Participants will answer questions in a location and time of their choosing. Upon receipt, study phones that are returned by participants will be factory reset. Phones will not be mined or reviewed for non-study related data.

### **18.0 Informed Consent Process**

The informed consent process will be completed via phone. During this call, study staff will verify that each individual meets the study inclusion criteria, staff will review study details with each individual; and interested individuals will complete the informed consent process (signatures will be collected digitally via REDCap).

The information to be provided to the participants over the phone will be that which is included in the uploaded consent document (please refer to consent form uploaded to the Local Site Documents). The consent document will be displayed to participants over REDCap and participants will be able to read and review all information while on the phone with a research assistant who will ensure the participant understands the research and has no questions. Thus, all participants will be provided with written information describing the research to be provided to the subject

The research will present no more than a Minimal Risk of harm to subjects and will not involve procedures for which written consent is normally required outside of the research context.

Participants will be informed that qualitative data collected through the qualitative interview will be transcribed through transcription company Civicom. Accordingly, Civicom will readily review and accept clients and partners ensuring that PHI shared with them will not be compromised, as they are committed to confidentiality and the protection of health information for individuals, clients, customers and partners. Moreover, we will ensure participants are aware the only data being shared with Civicom is the audio recording of qualitative interviews, and as such, no personal information will be shared with Civicom unless this information is mentioned during the interview process.

### **19.0 Process to Document Consent in Writing**

The consent form will be reviewed with the participant by a member of the study staff via phone. Participants who choose to take part in the research study will sign consent forms electronically via REDCap.

REDCap is a secure, web-based platform which allows for safe, secure and easy sharing of collected data within and across institutions for multicenter trials as it requires user authentication and can assign data access rights based on user role, allows for field-level data validation, and has mechanisms for ensuring data quality and integrity. It offers a digital method to acquire and store participant consent by implementing the study's consent form through an online survey that will display a PDF copy of the consent document (please refer to uploaded consent form in local site documents) that can be accessed by the participant through a computer, mobile phone, or tablet. Participants will be able to read and review the consent form virtually and will do so while on the phone with a research assistant who will ensure the participant understands the study procedures and who will answer any questions the participant may have.

**FULL PROTOCOL TITLE:** Mobile Health to Monitor Risk for COVID-19 and Improve Mental Health during the Pandemic

Participants who would like to participate will be able to ‘sign’ their consent form electronically by typing in their name or by utilizing REDCap’s ‘Signature’ field type on the survey. Signed documents will be protectively stored to our server and participants will not need to email any signed documents to the research team. Participants will be mailed a signed copy of the consent form.

## **20.0 Data Management**

Data Management Organizational Structure. Confidentiality is assured by several factors. Most importantly, participants will be identified only by participant identification number (names and ID numbers will be stored in encrypted and password protected data files on the investigators firewalled computers). Additional measures to ensure the confidentiality of study data include the following: access to databases (REDCap and InsightTM) will require complex passwords. When data are accessed, the user id, password, date, and time are logged. Each user of the systems will be assigned unique user-IDs.

Our study procedures prevent potential fraudulent surveys, as they consist of speaking with participants on the phone before they are enrolled, and all participants will need an activation code from the research team in order to participate in the study. Additionally, participants will need to provide a valid address, social security number, and date of birth in order to receive Greenphire cards.

The Insight app encrypts all data as it is collected and this data is synced to our secure servers up to four times per day. Thus, the research team can still access data collected through Insight even when a phone is not returned and may be retrieved if a phone is lost. Participant data will be collected through Insight, REDCap, and qualitative interviews will be recorded and transcribed. Recordings of transcribed interviews will be deleted within 12 months of transcription. All data will be stored in password protected and encrypted computers. The Insight app is encrypted within the smartphone.

A copy of the collected data will be stored for at least 3 years following completion of the research study. Study data will be stored to university owned encrypted computers. Consistent with NIH requirements, we will provide de-identified data from this project to interested individuals one year following achievement of the aims of the project (i.e., publication of the main outcome papers). These data will be provided in digital format (i.e., disk) with clear labels for all variables. Requested data will be released directly by the investigators providing evidence of their institutional IRB approval for planned analyses of the data. Our team will be available to address queries. The Insight app works through an encrypted shared content management system which allows researchers from both sites to download data directly to university owned encrypted computers. Both sites are able to download study data directly. Study data collected through Insight will be saved to our laboratory drive which is set up by the UH Psychology Department’s IT team. Study data will be password protected.

For recruitment through BuildClinical, they will be collecting their own data when advertising our study to participants and sharing data with the University of Houston and University of Oklahoma study teams. Data collection will be through our pre-screener link. Collected data will

**FULL PROTOCOL TITLE:** Mobile Health to Monitor Risk for COVID-19 and Improve Mental Health during the Pandemic

include: (1) Full name, (2) Phone number, (3) Phone number (secondary), (4) Email address, (5) Age, (6) Date of birth, (7) Ethnicity, (8) Race, and (9) Gender assigned at birth. BuildClinical does not interact with data outside of sending the data to the University of Houston and the University of Oklahoma. BuildClinical's Secure Socket Layer (SSL) software encrypts all inputted information and keeps the information private. All of BuildClinical's systems are HIPPA-compliant and have been approved by the Office of Veterans Affairs and the National Institutes of Health. Study teams will not be sharing data with BuildClinical that will need to be protected by the 3rd party. Upon request, BuildClinical can remove data from their platform.

Qualitative data collected through the qualitative interview will be transcribed through transcription company Civicom. Civicom acts as a Business Associate of Covered Entities as defined under HIPAA. Accordingly, Civicom will readily review and accept clients and partners ensuring that PHI shared with them will not be compromised. Moreover, Civicom is committed to confidentiality and the protection of health information for individuals, clients, customers and partners. Their data policies ensure that privacy and security of any health information is protected in all forms, with particular care in controlling the confidentiality, storage and access to electronic Protected Health Information. They have achieved this by implementing security standards, administrative, technical, and physical safeguards, organizational requirements, and requirements for documentation, policies and procedures. Civicom standards are maintained and improved by continuous review and audit of internal processes and business agreements, with the aid of external consultants and specialized staff dedicated to data privacy. Additionally, Civicom provides training to all members of its workforce on policies and procedures with respect to PHI, as necessary and appropriate for them to carry out their job responsibilities. Moreover, it must be noted that the only data being shared with Civicom is the audio recording of qualitative interviews, and as such, no personal information or PHI will be shared with Civicom unless this information is mentioned during the interview process of any participants.

Data analysis overview: Hypotheses for Aims 1 and 2 will be examined using latent growth models (LGM), multilevel structural equation models (MSEM) and latent difference score models using MPlus 8.0. To simplify subsequent sections, an overview of the common data analysis elements is presented first. Data will first be examined for multivariate normality and outliers to determine the most appropriate estimator. The maximum likelihood (ML) estimator will be used if data are approximately normal. Robust maximum likelihood (MLR) will be used if the data are not multivariate normal. We anticipate some participant attrition during the trial. Missing data will be handled in all analyses using direct ML techniques within MPlus under a missing at random (MAR) assumption. Modern missing data techniques such as direct ML increase statistical power and provide more accurate estimates of model parameters and standard errors and are the recommended intent-to-treat approach for clinical trials. LGM will generally be used to model outcomes collected at major assessments. MSEM will be used to further examine the longitudinal course of outcomes and hypothesized mechanisms of action as MSEM is ideally suited for disentangling within and between individual variance in order to more precisely estimate main effects, lagged effects, and indirect effects in intensive longitudinal designs. Evaluation of model fit in the LGM/MSEM models will be examined using fit diagnostics (i.e., standardized residuals) and common fit statistics (i.e., root mean square error of approximation) following the associated cutoff criteria recommended by Hu & Bentler. We will assess the equivalence of the treatment groups on key baseline

**FULL PROTOCOL TITLE:** Mobile Health to Monitor Risk for COVID-19 and Improve Mental Health during the Pandemic

variables (demographics and psychological variables); variables on which the groups differ will be used as covariates in the final analyses. We will also examine attrition from the study as a dichotomous outcome and use logistic regression to determine if treatment assignment predicts attrition.

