**Assessment Schedule:**

Table 3. MEASURES for Phase 1

MEASURE	ITEMS	FULL BATTERY ASSESSMENTS			EMA ASSESSMENTS		
		Screen	Base	3- and 6- Month FU			
EASE Measures							
Descriptive Variables and Moderators							
Demographics-Treatment History Questionnaire (DTHQ; descriptive)	24	24			Sleep (4)		
Additional Phone Screener Items	4	4			Alcohol Consumption		
6CIT (eligibility)	7	7			Cigarette Consumption		
Rapid Estimate of Adult Literacy in Medicine-Short Form  (eligibility)	9	9			Marijuana Use		
Demographic/Background Information Questionnaire	21		21	2 (6- Month FU Only)	Fast food consumption		
Sheehan Disability Scale (SDS)  (A.1: H1)	4		4	4	Other Substance Use SSASI (2)		
System Usability Scale (A.3)	10			10	Prescription Medication Consumption		
4-item Perceived Stress Scale	4		4	4	Discrimination Experience (3)		
Everyday Discrimination Scale (EDS)  (A.2: H3)	6		6	6	Affect (15)		
					Pain Level		

**FULL PROTOCOL TITLE:** Mobile Health to Monitor Risk for COVID-19 and Improve Mental Health during the Pandemic

Coronavirus Racial Bias Scale (CRBS)  (A.2: H3)	4		4	4	Ability to Cope with Stress
The Patient Health Questionnaire-4 (PHQ-4)	4		4	4	Social Support
Health Related Quality of Life (HRQOL)	3		3	3	Location
The Perceived Social Support Questionnaire (F-SozU K-6) (A.2: H3)	6		6	6	Evening Daily Diary
MacArthur Scale of Subjective Social Status (A.2: H.4)	2		2	2	Physical Activity (2)
COVID 19 Vaccine Hesitancy Survey	15		15	15	News
Additional Aim 1 Measures	4		4	4	Money
Financial strain questionnaire	9		9	9	Hours Away from Home
Behavioral Risk Factor Surveillance System (BRFSS) Inadequate Sleep Questionnaire	5		5	5	Course of your day (2)
Frequency of Attendance at Religious Services	2		2	2	Amount eaten
PEG Scale  (A.3)	3		3	3	Argument
Affect Constructs					
Overall Anxiety Severity and Impairment Scale (OASIS)  (A.1: H1)	5	5	5	5	Pain Level
Overall Depression Severity and Impairment Scale (ODSIS)  (A.1: H1)	5	5	5	5	Ability to Cope with Stress
SSASI  (A.2: H3)	5		5	5	Location
Discrimination Burden (A.2: H.4)	4		4	4	Sunday Morning Diary
Self-Rated Health Questionnaire	33		33	21	Self-rated health questionnaire
Employment Status (A.3.b)	3		3	3	Optimism towards the future
Fear of COVID-19  (A.2: H3)	5		5	5	App Quality (3)

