COVID-19 Psychological Impact Survey	3		3	3	OASIS (5)
Daily Activities (A.1: H.1)	3		3	3	SSASI (5)
Change in Fast Food Consumption during COVID-19	1		1	1	PSI (8)
COVID-19 Substance Use (A.3.b)	4		4	4	ODSIS (5)
AUDIT-C	3		3	3	Report Distress
Marijuana/Cannabis Use Behavior	6		6	6	Affect (15)
Abbreviated Multidimensional Acculturation Scale (A.2)	15		15	15	Location
LEC5 & PCPTSD-5	6		6	6	Pain Level Ability to Cope with Stress
Three-item Loneliness Scale	3		3	3	
Mindful Attention Awareness Scale (MAAS)	15		15	15	Report COVID-19 Symptoms
Total items	273	54	209	188	Current Symptoms Exposure to someone with COVID Loss of taste/sense of smell

Note. Screen = REDCap or Phone Screener; Base = Baseline; 3- and 6-Month FU = 3- and 6-Month Post-Baseline Follow-up. \*Indicates items that are only collected during the morning EMA. \*\*Indicates items that are only collected during the evening EMA. Please see EMA types below for more information.

**EASE App Features and Treatment Components.** See Table 2 for app components. EASE offers

**Table 2.** Comparison of EASE and Control conditions

App Components	EASE	Control
EMA	X	X (add on for this study)
COVID-19 monitoring and intervention	X	X (add on for this study)
AS psychoeducation	X	
On demand tips and exercises		
Coping with mood	X	X
Coping with stress	X	X
Interoceptive exposure	X	
Guided relaxation	X	X
Inspirational messages	X	
Challenge Automatic	X	

**FULL PROTOCOL TITLE:** Mobile Health to Monitor Risk for COVID-19 and Improve Mental Health during the Pandemic

clinical grade care by integrating standard CBT with a transdiagnostic treatment for AS reduction. Individuals randomized to the EASE group will receive: 1) scheduled treatment, 2) scheduled and cued interoceptive exposure sessions, 3) on-demand intervention content (i.e., how to cope with symptoms of anxiety and depression; cognitive restructuring exercises; guided relaxation videos), and 4) tailored treatment messages based on responses to EMA items. Information about frequency of resource use and length of time spent viewing EASE intervention content will be collected through Insight™.

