app from the research team. The control app was built using the Insight platform. Participants assigned to the control app will have access to: 1) a series of educational videos that discuss meditation techniques, mindfulness exercises, and stress reduction exercises, 2) a feature that allows participants to report when they are experiencing heightened stress, anxiety or depression, and 3) a “Report COVID-19 Symptoms” button that allows participants to report any COVID-19 symptoms they are experiencing to research staff at any time throughout the study. If a symptom cluster consistent with COVID-19 is detected, an encrypted email will be sent to the research team and they will work with the participant to help them find a local testing center. Instructions on how to use the app will be available to participants on the home screen, and will accessible at all times. Additionally, participants will be able to call study staff by pressing the “Call Staff” button on the study home screen. Participants will receive 2 daily EMAs during which they will be prompted to watch aforementioned educational videos twice per week. Following the intervention period, participants will be encouraged to continue to practice the meditation, mindfulness, and stress reduction techniques they have learned, report moments of heightened stress, depression, or anxiety, and report any COVID-19 symptoms they experience.

**Ecological Momentary Assessments (EMA).** EMAs are currently the most accurate way to measure phenomena in real-time, natural settings. EMA items will identify fluctuations in key variables that predict study outcomes with less bias than traditional in-person assessments. EMA data will be used to identify moments of distress (e.g., anxiety/depression), tailor EASE treatment, and identify treatment mechanisms.

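### The analysis overview does not name the weekly OASIS/ODSIS as auxiliaries in the three-visit LGM, so arm-specific dropout tied to between-visit symptoms could bias the contrast modestly and go unseen by the arm-only attrition check

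*Combined protocol and SAP*

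**What the plan says.** Section 20.0, Data analysis overview, sets one rule for missing data: "Missing data will be handled in all analyses using direct ML techniques within MPlus under a missing at random (MAR) assumption". For the visits at baseline, 3 and 6 months, "LGM will generally be used to model outcomes collected at major assessments". A second model, the multilevel SEM (MSEM), is planned for the longitudinal course and mechanisms, "in order to more precisely estimate main effects, lagged effects, and indirect effects in intensive longitudinal designs". The one attrition check is to "use logistic regression to determine if treatment assignment predicts attrition". The text describes its own scope: "an overview of the common data analysis elements is presented first".

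Section 10.0 shows what is measured between visits. In Table 3 the block headed "Sunday Morning Diary" lists the full five-item OASIS and ODSIS, the two symptom measures tagged to Aim 1, H1. Time-based EMAs run for six months. Control participants get them too: Table 2 marks the EMA row for Control as "X (add on for this study)", and the description of the control app says "Participants will receive 2 daily EMAs during which they will be prompted to watch aforementioned educational videos twice per week".

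The public text names no auxiliary variable for the LGM and does not relate attrition to symptoms.

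**The concern.** MAR is a statement about the variables in the likelihood. Direct ML on three visits handles dropout that depends on observed baseline or 3-month scores, even if that dependence differs by arm. It does not handle dropout that depends, differently by arm, on how participants felt between visits beyond what the visit scores carry. The weekly OASIS and ODSIS record exactly that. With those scores in the model, such dropout becomes approximately ignorable; without them it is not.

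At stake are the 3- and 6-month OASIS and ODSIS contrasts for H1. The planned attrition check compares dropout rates between arms. It does not ask who drops out.

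**Working it through.** **Inputs from the documents.** 440 per arm (5.0; Aim 1 says 420). Retention of 80-90% at each follow-up (8.0), so 10-20% missing, with no rate by arm. EMA compliance of about 70% in earlier trials (10.0, EMA Types). The documents give no effect size, SD, alpha or power for this analysis, so there is no planned figure to reproduce.

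**Assumed.** Unit-SD scores. Correlations: baseline-weekly 0.50, baseline-3 months 0.45, baseline-6 months 0.40, weekly-3 months 0.70, weekly-6 months 0.55, 3-6 months 0.60. Dropout before month 3 is logistic in the latest weekly score with slope *b* (log-odds per SD). Two-sided 5% tests.

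**Step 1: hand approximation.** With dropout rate *p*, logistic dropout shifts the mean weekly score of those observed by about −*b·p*. Conditioning on baseline leaves −*b·p*·(1 − r_BW²). The slope of the 3-month score on the weekly score given baseline is (r_W3 − r_B3·r_BW)/(1 − r_BW²). Multiplying and differencing the arms:

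bias ≈ −(b_E·p_E − b_C·p_C)·(r_W3 − r_B3·r_BW), with 0.70 − 0.45 × 0.50 = 0.475.

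Equal slopes and rates cancel. For EASE only, *b* = 0.5 and *p* = 0.10: −0.5 × 0.10 × 0.475 = −0.024.

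**Step 2: simulation.** 400,000 per arm, unstructured direct ML standing in for the LGM, slope in EASE only, equal dropout rates. SE and coverage are for 440 per arm.

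| | 10%, b=0.5 | 10%, b=1.0 | 20%, b=0.5 | 20%, b=1.0 |
|---|---|---|---|---|
| Hand approximation, 3 months | −0.024 | −0.048 | −0.048 | −0.095 |
| Simulated bias, 3 months | −0.023 | −0.039 | −0.050 | −0.082 |
| Simulated bias, 6 months | −0.017 | −0.032 | −0.038 | −0.062 |
| 3-month bias / SE | 0.37 | 0.73 | 0.67 | 1.26 |
| Implied 95% CI coverage | 93.4% | 88.6% | 89.7% | 75.6% |
| 3 months, weekly added, 70% available | −0.010 | −0.007 | −0.016 | −0.021 |
| 3 months, weekly added, 70% of stayers and 50% of dropouts | −0.011 | −0.022 | −0.020 | −0.037 |
| 3 months, weekly added, no dropout has one | −0.023 | −0.045 | −0.044 | −0.088 |

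A repeat gave 0.02-0.04 SD at 10% and 0.05-0.09 SD at 20%, falling to about 0.00-0.03 with 70% of weekly scores. A separate simulation fitted a linear LGM to a weekly process (assumed SD 4 points, slopes 1 vs 0). Its 6-month bias at 20% attrition was 0.21-0.35 points, and 0.21/4 to 0.35/4 is 0.05-0.09 SD.

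**Step 3: when the bias vanishes or changes.** Same slope and rate in both arms: within 0.001. Dropout driven by baseline, or month-6 missingness driven by the observed 3-month score: at most 0.006, which is simulation noise. If improvers leave instead, the sign flips (+0.026 to +0.085). If dropout depends on the unseen 3-month score itself, bias of 0.04-0.14 falls only to 0.03-0.11 with weekly scores.

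**Step 4: the arm-only check.** With *n* = 440 per arm,

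z = [|p₁ − p₂| − 1.96·√(2p̄(1 − p̄)/n)] / √[(p₁(1 − p₁) + p₂(1 − p₂))/n].

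For 10% vs 20%: (0.100 − 1.96 × 0.02407)/0.02384 = 2.22, so power is 98.7% (98.3% at 420). Likewise 10 vs 15% gives 61%, 15 vs 20% gives 50%, 17 vs 20% gives 21% and 10 vs 12% gives 16%. At equal rates it rejects at alpha, about 5%, however strongly symptoms drive dropout in one arm.

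**Step 5: an extended check.** A natural extension regresses attrition on the latest available weekly score. Dropouts' latest scores are taken earlier than completers', so if symptoms improve over time, dropouts look worse through timing alone. With dropout completely at random and improving symptoms, the latest-score term was significant in 64-100% of simulated trials and its arm interaction in 5-31%. When timing is not an issue and all scores are observed, the arm-by-weekly-score test has 57/99% (10% attrition) and 80/100% (20%) power at slopes 0.5/1.0 without baseline terms. With baseline and arm-by-baseline it has about 47/95% and 69/99%. At 70% availability with baseline terms it has 35/87% and 55/98%.

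**The case against.** The strongest reply has four parts.

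- **Unseen text.** The overview announces later sections that are not in the public text and that could name auxiliaries. This stands. The point covers only what the overview states; a reader might infer that the trial has no such plan, and the documents do not show that.
- **MSEM.** It may use the weekly scores, and direct ML applies there too. That is fair, but the overview presents MSEM as further examination and does not link it to missing values in the LGM.
- **Hypothetical mechanism.** The bias needs symptom-driven dropout that differs by arm, and no passage reports any. Daily alerts, calls, texts and emails are planned to limit missed follow-ups. A reader might infer that the LGM contrast is biased; the documents support only that it could be. At 10% missing and slope 0.5, coverage is still 93%.
- **The attrition check.** It is not offered as a test of MAR. A reader might also infer that it lacks power in general. It does not: power is about 99% for 10% vs 20% and 50-61% for the 5-point gaps computed. Even so, a positive result shows a difference in rates, not a link to symptoms.

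In addition, EMAs and follow-ups run through one app, so dropouts may lack recent weekly scores. This limits the benefit of the remedy and is carried into the conclusion.

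**Conclusion.** The point holds as a modest one. The overview leaves repeated OASIS and ODSIS scores, already collected in both arms, out of the stated LGM likelihood. If dropout follows between-visit symptoms differently by arm, the 3-month contrast is off by about 0.02-0.04 SD at 10% missing and 0.05-0.09 SD at 20%. At 440 per arm that is about 0.4-0.7 and 0.7-1.3 standard errors. The sign is unknown, and the sizes rest on assumed slopes and correlations. Bias is about zero if the arms share slope and rate, or if dropout depends only on observed visit scores.

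The arm-only regression cannot show symptom-dependent dropout and has little power when attrition rates are similar between arms. Weekly auxiliaries remove most of the bias if dropouts have weekly scores, and none if they do not.

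**What to change.** 1. In the OASIS and ODSIS LGMs, name the weekly Sunday OASIS and ODSIS (for example as 4-week block means) as auxiliary variables.
2. Report, by arm, how many dropouts have weekly scores, so readers can judge how much the auxiliaries could correct.
3. If the attrition check is extended, use time-aligned scores: for example a discrete-time dropout model with lagged weekly score, week, baseline and their interactions with arm. Do not use the latest available score. Any power quoted should match the fitted model: the 57-100% from a model without baseline terms does not apply once they are included (about 47-99% with all scores observed, less with missing scores). Neither range was computed for the discrete-time model.
4. Optionally, add one arm-specific delta-adjusted sensitivity analysis of the LGM contrast for dropout that remains non-ignorable.

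The cost is SAP wording and modest extra Mplus work, with no new data. The downside is a larger model, with no gain for participants who stop EMAs and follow-ups together.
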